1.7 Blinding and Randomization Methods

1.7.1 Blinding Method

Subjects, investigators, and the Sponsor's study team members will remain blinded to the treatment assignment in the randomization phase. The investigator will not be provided with randomization codes nor the treatment assigned and received. The codes will be maintained within the IRT System, which has the functionality to allow the investigator to break the blind for an individual subject if necessary, to appropriately manage or treat the subject. Data that may potentially unblind the treatment assignment (e.g., study drug plasma concentrations) will be handled with special care to ensure that the integrity of the blind is maintained and the potential for bias is minimized.

1.7.2 Randomization Method

The randomization of the treatment assignment will be stratified by the following factors and implemented using the IRT System:

- Number of prior lines of therapy $(1-2 \text{ vs.} \ge 3)$
- ECOG performance status (0-1 vs. 2)
- TLS category (low risk vs. increased risk)

Within each of the eight randomization strata, subjects will be randomly assigned at a 1:1 ratio to the two treatment arms based on permuted block size.

Page 14 of 35

2 GENERAL ANALYSIS CONSIDERATION

The statistical analysis sections in this SAP are mainly for the double-blind Randomization Phase. All data collected for the subjects in the SRI portion will only be summarized with descriptive statistics or listed separately from Phase 3 data. In addition to standard summaries for TEAEs, the safety summary included for SRI subjects will be limited in scope to DLTs and TLS.

Subjects in the randomization phase will be analyzed and summarized by treatment as randomized for efficacy endpoints and as treated for safety.

Subgroup analyses are mainly to evaluate trend and assess the internal consistency of any treatment benefit and/or safety signal. Forest plots of hazard ratios and associated confidence intervals will be provided for each category of the subgroup variable to show the trend. Statistical tests will not be performed for the subgroup analysis.

General Definitions:

The date of the first dose of study treatment is defined as the date the subject received the first dose of ibrutinib or venetoclax/placebo (whichever occurs first), and the date of the last dose of study treatment is defined as the date the subject received the last dose of ibrutinib or venetoclax/placebo (whichever occurs later).

Unless otherwise specified, the baseline value is defined as the last non-missing valid value collected prior to the first administration of study treatment. For subjects who have been randomized but not treated, the randomization date will be used as the reference date for the baseline.

For the Safety Run-in Period, the TLS/DLT assessment period is defined as the standard Ramp-up Period with a minimum of 5 weeks. The DLT period ends on the 7th day of 400 mg venetoclax.

2.1 Analysis Sets

Intent-to-Treat Population in Randomization Phase

The intent-to-treat (ITT) population includes all subjects randomized into the study.

Safety Population

The safety population (SP) includes all subjects who received at least one dose of study treatment (ibrutinib or venetoclax/placebo).

Safety Run-in Period Evaluable Population

Subjects who did not complete the TLS and DLT assessment period for any reason other than TLS or a DLT or subjects who missed ≥20% of the planned doses of ibrutinib or venetoclax for reasons other than toxicity (e.g., non-compliance, withdrawal of consent, or disease progression) during the TLS/DLT assessment period will be considered non-evaluable. All other enrolled subjects in the Safety Run-in Period will be considered evaluable for the TLS/DLT assessment.

2.2 Definition of Subgroups

Analyses for the baseline subgroups will be performed for selected variables. The baseline subgroup variables (Table 1) and the cutoff values are subject to change (if warranted) to better represent the data,

 Table 1
 Baseline Subgroups

Baseline Subgroup	Definition of Baseline Subgroup	Analysis Type
Age	< 65, ≥ 65	E, S
Gender	Male, Female	E, S
Race	White, Non-White	E, S
Geographic region	North America, Europe, Asia Pacific	B, E, S
Number of prior lines of therapy (1-2 vs. ≥3) per CRF	1-2, ≥ 3	Е
ECOG performance status per CRF	0, 1-2	Е
TLS risk category per CRF	Low Risk, Increased Risk	Е
Simplified MIPI score	Low Risk, Intermediate Risk, High Risk	Е
Bulky tumor (largest long diameter) per investigator	< 5 cm, ≥ 5 cm	Е
Enlargement of spleen per investigator	Yes, No	Е
Extranodal disease per investigator	Presence, Absence	Е

Page 16 of 35

Baseline Subgroup	Definition of Baseline Subgroup	Analysis Type
Blastoid variant and/or pleomorphic variant of MCL	Yes, No	Е
Blastoid variant of MCL	Yes, No	Е
TP53 Mutation	Mutated, Not Mutated, Not Performed/Missing	Е
Prior stem cell transplant (SCT)	Yes, No	Е
Renal function (creatinine clearance)	< 60 mL/min, ≥ 60 mL/min	S
Hepatic function (NCI ODWG definition)	normal, mild, moderate, severe (or normal vs. abnormal as appropriate)	S

Analysis type: B=Subject Demographics, Baseline Characteristics, Baseline Disease Characteristics; E = Efficacy (PFS); MIPI: MCL International Prognostic Index; MRD: Minimal Residual Disease; NCI ODWG: NCI Organ Dysfunction Working Group Liver Function Classification (Ramanathan et al, 2008); S = Safety (Overview TEAE, TEAE by SOC/PT, Grade 3 or higher TEAE by SOC/PT).

3 SUBJECT INFORMATION

3.1 Subject Disposition

Subject enrollment will be summarized by geographic region, country and site. Subject disposition for each study drug and for study participation will be tabulated. Overall treatment duration and time on study will be summarized by treatment arm.

The disposition tables will include the following summaries by treatment arm and overall:

- Analysis populations (all subjects)
- Enrollment by geographic region, country and investigator (ITT population)
- Summary of randomization stratification per IRT (ITT population)
- Study Treatment Disposition and Discontinuation (ITT population)
- Study Status, Duration of Treatment and Study Exit (ITT population).

Time on study is calculated based on reverse Kaplan-Meier estimates of the overall survival follow-up time (i.e., subjects who died will be censored at the death date for the time on study).

3.2 Demographics, Baseline Characteristics, and Baseline Disease Characteristics

Subject demographics, baseline characteristics, and baseline disease characteristics including but not limited to age, gender, race, etc., will be summarized with descriptive statistics for the ITT population by treatment arm.

3.3 Prior and Concomitant Medications

Medications will be coded to a generic name and an Anatomical Therapeutic Chemical (ATC) class according to the World Health Organization drug dictionary (WHODRUG B3 Mar 2021).

Prior medications are defined as medications that started prior to the date of the first dose of study treatment. Concomitant medications are defined as medications that were taken on treatment (i.e., from the date of the first dose of study treatment through the date of the last dose of study treatment).

Concomitant medications will be summarized by ATC class and preferred term (PT) by treatment arm based on the Safety Population. Each subject will be counted only once overall, for each PT, and for each ATC class.

The following concomitant medications will be summarized separately:

CYP3A inhibitors and inducers

- Anticoagulants and antiplatelet agents
- Blood supportive products and intravenous immunoglobulin (IVIG)
- Growth factors

3.4 Extent of Exposure to Study Treatment

Exposure to study treatment will be summarized by treatment arm for the Safety Population. Descriptive statistics will be provided for the following data for each study drug (ibrutinib and venetoclax/placebo): treatment duration, total cumulative dose administered, dose intensity (average daily dose), and relative dose intensity (%) based on the entire treatment period (including both the ramp-up period and fixed dose period), and number (%) of subjects with a dose reduction or dose hold due to adverse events (AEs). In addition, dose modification of venetoclax due to CYP inhibitor will be summarized based on the check box on the Study Drug Administration page.

Planned dose intensity (PDI) for each study drug is calculated as below:

Ibrutinib:

Planned dose intensity (PDI) for ibrutinib is 560 mg per day.

Venetoclax/placebo:

Regardless of response assessment, Venetoclax/placebo will be discontinued after 104 weeks of treatment including 5 weeks of the standard dose ramp-up period (20 mg, 50 mg, 100 mg, 200 mg, and 400 mg weekly, respectively) and approximately 99 weeks of the fixed dose (400 mg) period.

The planned dose intensity (mg/day) for venetoclax/placebo is calculated as the total amount of the planned dose (mg) during the maximum treatment period allowed (104 weeks) divided by the duration of the maximum treatment period allowed (104 weeks):

$$388.2 \, mg/day = \frac{(20 + 50 + 100 + 200 + 400) \, mg \times 7 \, days + 400mg \times (104 \times 7 - 35) \, days}{104 \times 7 \, days}$$

For each study drug, the actual dose intensity (ADI) (mg/day) is calculated as the total amount of dose (mg) received during the entire treatment period divided by the entire treatment duration (day), and the relative dose intensity (RDI) (%) is calculated as the (actual dose intensity/planned dose intensity)*100%.

Page 19 of 35

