5.3.2.3 Dose and Administration

Venetoclax/placebo tablets should be taken orally once daily with a meal and water at approximately the same time each day with ibrutinib capsules. Venetoclax/placebo tablets should be swallowed whole and not chewed, crushed, or broken prior to swallowing. If the subject misses a dose of venetoclax/placebo within 8 hours of the time it is usually taken, the subject should take the missed dose as soon as possible on the same day and resume the normal daily dosing schedule. If a subject misses a venetoclax/placebo dose by more than 8 hours, the subject should not take the missed dose and resume the usual dosing schedule the following day. The use of strong CYP3A inhibitors/inducers, and grapefruit and Seville oranges should be avoided for the duration of the study (Appendix D).

For subjects starting with the concurrent administration of ibrutinib and venetoclax using the standard Ramp-up Schedule, venetoclax/placebo will be delivered in the clinic on Days 1, 2 (all subjects) and 3 (hospitalized subjects) of Weeks 1 and 2; on Days 1 of the remaining weeks during the Ramp-up Period (see Section 8.2); and on the PK sample collection day (see Section 7.1.4.1 and Section 7.1.4.2). Otherwise, venetoclax dosing will be done on an outpatient basis. Subjects should strictly adhere to the Ramp-up Schedule. In the event of TLS, dosing of venetoclax will be withheld and/or modified per the protocol and may be resumed at the investigator's discretion, when all laboratory abnormalities have returned to baseline. If venetoclax is resumed at the same dose level, the 7-day count should be re-started. In cases of vomiting after taking venetoclax/placebo, no additional dose (tablets) should be taken that day. The next dose should be taken at the usual time the following day.

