5.4 Criteria for Permanent Discontinuation of Study Drug

Investigators are encouraged to keep a subject who is experiencing clinical benefit in the study unless significant toxicity puts the subject at risk or routine noncompliance puts the study outcomes at risk. Subjects who discontinue either ibrutinib or venetoclax/placebo (but not both) for tolerability issues may continue in the study as long as they are receiving at least one study drug. For a complete list of criteria for permanent discontinuation of study treatment, refer to Section 9.2.

An End-of-Treatment Visit (Section 8.2.3) is required for all subjects except for those subjects who have withdrawn full consent.

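### Venetoclax/placebo relative dose intensity compares a subject's own-duration average dose with a fixed 104-week average, so fully adherent subjects who stop early score below 100%

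*SAP*

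**What the plan says.** SAP Section 3.4 summarises exposure by arm and by drug, and includes RDI over the whole treatment period, ramp-up included. For venetoclax/placebo the planned schedule is "20 mg, 50 mg, 100 mg, 200 mg, and 400 mg weekly, respectively", followed by "approximately 99 weeks of the fixed dose (400 mg) period". The planned dose intensity (PDI) is then "the total amount of the planned dose (mg) during the maximum treatment period allowed (104 weeks) divided by the duration" of that same period, given as 388.2 mg/day.

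The actual dose intensity (ADI) is "the total amount of dose (mg) received during the entire treatment period divided by the entire treatment duration (day"). RDI is ADI divided by PDI, expressed as a percentage. Nothing adjusts the PDI for a subject who stops before 104 weeks.

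The SAP gives these definitions for each study drug, but the only first and last dose dates it defines, in Section 2, span both drugs. The last dose of study treatment is "the date the subject received the last dose of ibrutinib or venetoclax/placebo (whichever occurs later").

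Protocol Section 5.4 allows one drug to be stopped alone: "Subjects who discontinue either ibrutinib or venetoclax/placebo (but not both) for tolerability issues may continue in the study" while receiving at least one study drug.

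**The concern.** RDI is normally read as the share of the scheduled dose that was taken while on drug. Here the numerator averages over the subject's own time on drug and the denominator over 104 weeks. The two periods agree only for a subject treated for exactly 104 weeks. For anyone who stops sooner, the planned ramp-up pulls the numerator down much more than the denominator, so RDI shows a dose loss where none occurred.

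The subjects affected are those who stop venetoclax/placebo early, and for them the reason for a low dose intensity matters most. The ibrutinib PDI is a constant 560 mg/day with no ramp-up, so this mismatch does not arise there. Two figures reported under the same label for the two drugs would then measure different things.

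A smaller point concerns the duration itself. Section 3.4 points to a drug-specific duration but does not define one. A programmer who used the dates in Section 2 would divide venetoclax dose by time on either drug.

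**Working it through.** **Inputs (SAP Section 3.4).** Ramp-up of 20, 50, 100, 200 and 400 mg/day for 7 days each; then 400 mg/day; maximum 104 weeks = 728 days. ADI is taken over the subject's own time on venetoclax/placebo.

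**The SAP's own figure.** Ramp-up total = (20 + 50 + 100 + 200 + 400) × 7 = 5,390 mg. PDI = (5,390 + 400 × 693) / 728 = 282,590 / 728 = 388.17 mg/day. This reproduces 388.2.

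**RDI of a subject who takes every scheduled dose and stops on day d (d ≥ 35).**
ADI = [5,390 + 400 × (d − 35)] / d; RDI = ADI / 388.17 × 100%.

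| Stop at week | Day | ADI (mg/day) | RDI |
|---|---|---|---|
| 5 | 35 | 154.0 | 39.7% |
| 8 | 56 | 246.2 | 63.4% |
| 13 | 91 | 305.4 | 78.7% |
| 16 | 112 | 323.1 | 83.2% |
| 26 | 182 | 352.7 | 90.9% |
| 39 | 273 | 368.5 | 94.9% |
| 52 | 364 | 376.3 | 97.0% |
| 78 | 546 | 384.2 | 99.0% |
| 104 | 728 | 388.2 | 100% |

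RDI first reaches 80% on day 97 and 90% on day 171 (about week 24).

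**Two different histories, one score.**
- Full adherence, stop on day 81: (5,390 + 400 × 46) / 81 = 23,790 / 81 = 293.7 mg/day; 293.7 / 388.17 = 75.7%.
- Full ramp-up, then 300 mg from day 36 to week 104: (5,390 + 300 × 693) / 728 = 213,290 / 728 = 293.0 mg/day; 293.0 / 388.17 = 75.5%.

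**Arm-level illustration.** The documents give no distribution of time on venetoclax/placebo. Suppose, for scale only, that it is exponential with the PFS planning medians (14 and 23 months, 30.44 days per month), cut off at day 728, with full adherence. Mean RDI is then 89.4% vs 93.2%, and median RDI 97.9% vs 99.9%. If 10% of the 23-month arm instead stops evenly over days 1 to 91, its mean falls to 88.5%, below 89.4%. The direction is therefore not determined.

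**Duration across both drugs.** With the Section 2 dates, a subject who completes 104 weeks of venetoclax and stays on ibrutinib to week 156 would score 104 / 156 = 66.7%.

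**Own-duration version.** RDI = cumulative dose taken / cumulative scheduled dose to day d.
- Any fully adherent subject: 100%.
- The sustained 300 mg case: 213,290 / 282,590 = 75.5%, unchanged.
- One repeated 100 mg week, stop at week 13: dose taken = 7 × (20 + 50 + 100 + 100 + 200 + 400 + 7 × 400) = 25,690 mg; scheduled = 5,390 + 400 × 56 = 27,790 mg; RDI = 92.4%. The current formula gives 25,690 / 91 / 388.17 = 72.7%.
- The same repeat, completing week 104: 280,490 / 282,590 = 99.3% under both formulas.

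**The case against.** The SAP states the fixed 104-week denominator openly, and 388.2 is computed correctly. This is a prespecified convention for a descriptive quantity that feeds no endpoint, test or decision rule, and it is the same in both arms. Other planned outputs give the missing context: treatment duration, cumulative dose, average daily dose and AE-related reductions or holds by drug (SAP Section 3.4), disposition by drug (Section 3.1), and adverse events leading to discontinuation or dose change (Section 5). The day-81 subject and the 300 mg subject differ plainly in duration and cumulative dose. Shortfalls above 20 points are confined to the first 96 days, and in the illustration above the medians are close to 100%. The 66.7% case rests on a reading that the wording in Section 3.4 points away from.

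Most of this stands as a limit on weight. The point is definitional, its practical effect may be small, and the duration issue needs only a clarifying clause. It does not rescue the formula. The neighbouring outputs do not correct a subject's RDI or the mean and median built from it. Nor can the fixed denominator be defended as a way to capture early stopping: a subject who stops at week 78 forgoes 26 of 104 weeks and still scores 99.0%. As written, the ratio measures neither delivery against the 104-week plan nor adherence while on drug.

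**Conclusion.** The concern holds. For venetoclax/placebo, the stated rule gives an RDI below 100% to every fully adherent subject who stops before week 104. The shortfall is about 21 points at week 13, 9 at week 26, 3 at week 52 and 1 at week 78.

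This rests on reading the treatment duration as the subject's own time on venetoclax/placebo, which the by-drug wording of Section 3.4 supports, and on the SAP's planned ramp-up being followed. No hypothesis test is affected. The arms are distorted differently only if their stopping times differ, and the documents fix neither the size nor the direction of such a difference. It should be corrected because RDI is reported by arm and, as defined, can present early stopping as under-dosing.

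**What to change.** In SAP Section 3.4, define for each subject the planned cumulative venetoclax/placebo dose as the SAP's own schedule (ramp-up, then 400 mg) summed over that subject's treatment duration, from first to last venetoclax/placebo dose. Set RDI = actual cumulative dose / planned cumulative dose × 100%. State that the duration is drug-specific and not taken from the both-drug dates in Section 2. Use the same duration above and below the line, with no separate cap on the planned dose. With a cap, an adherent subject who runs to 106 weeks would score (5,390 + 400 × 707) / 282,590 = 102.0%.

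Add a footnote that permitted repeats of ramp-up weeks still lower RDI. Protocol Section 5.3.2.3 says "If venetoclax is resumed at the same dose level, the 7-day count should be re-started", and Section 5.3.2.5 allows ramp-up levels to be repeated after a long interruption. The ibrutinib planned dose intensity needs no change on this account.

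The cost is one formula and one footnote. It uses dosing data already collected, and alters no test, dose or clinical rule.

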3.5 Prior and Subsequent Anti-Cancer Treatments

Anti-cancer treatment includes anti-cancer drug therapies, anti-cancer radiation, and anti-cancer transplant/immunotherapy.

Prior anti-cancer treatments are anti-cancer treatments received prior to study treatment and will be summarized using the ITT population. Subsequent anti-cancer treatments are anti-cancer treatments received after the date of the last dose of study treatment and will be summarized using the Safety Population.

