6.2.5 Prohibited Concomitant Medications and Products for Ibrutinib and/or Venetoclax/placebo

Any non-study protocol-related chemotherapy, anticancer immunotherapy, experimental therapy, or radiotherapy are prohibited while the subject is receiving ibrutinib treatment.

Corticosteroids for the treatment of the underlying malignancy are prohibited (refer to Section 6.1 for further guidance).

The Sponsor must be notified in advance (or as soon as possible thereafter) of any instances in which prohibited therapies are administered.

Subjects may not consume grapefruit or grapefruit products, Seville oranges (including marmalade containing Seville oranges) or star fruit within the 3-day period prior to the first ibrutinib and venetoclax administration and until the last day of treatment is completed due to possible CYP3A mediated metabolic interaction.

Do not administer live attenuated vaccines prior to, during, or after treatment with venetoclax. The safety and efficacy of immunization with live or attenuated viral vaccines during or following venetoclax therapy have not been studied. Advise subjects that vaccinations may be less effective.

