10.2.3 Randomization Phase Secondary Endpoints

Efficacy:

- Complete response rate (CR) based on the best overall response per investigator assessment according to the Revised Response Criteria for Malignant Lymphoma (Cheson 2014).
- Overall response rate (ORR), defined as CR or PR per investigator assessment according to the Revised Response Criteria for Malignant Lymphoma (Cheson 2014).
- MRD-negative remission rate in subjects who achieve CR per investigator assessment. A MRD-negative remission is defined as undetectable MRD at documented CR in subjects who were MRD positive at screening as assessed by flow cytometry in bone marrow and/or peripheral blood, with requirement of confirmation of MRD negativity in the subsequent peripheral blood 12 weeks later. OS, defined as the time from randomization to death from any cause.
- DOR, defined for subjects who achieve an overall response as the time from the first occurrence of response (CR or PR) to disease progression or death, whichever occurs first.
- TTNT, defined as the duration from the date of randomization to the start date of any anti-lymphoma treatment subsequent to study treatment.

Safety:

- Frequency, severity, and relatedness of AEs
- Frequency, severity and management of TLS
- Frequency of AEs requiring discontinuation of study drug or dose reductions, or leading to death

Pharmacokinetics:

- Pharmacokinetics of ibrutinib at steady state
- Pharmacokinetics of venetoclax at steady state

Patient Reported Outcomes (PRO):

• Time to worsening in FACT-Lym subscale of the health-related quality of life questionnaire (FACT-Lym)

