1) To address the intercurrent events of use of subsequent anticancer therapy, hypothetical strategy (subjects who received subsequent anti-cancer treatment will be censored at the last adequate post-baseline disease assessment showing no evidence of PD prior to the initiation of subsequent anti-cancer treatment) is implemented.
2) Subjects who missed two or more consecutive overall disease assessments (algorithm is described in Appendix 1) prior to the PFS event will be censored at the last adequate post-baseline disease assessment showing no evidence of PD prior to the first missed disease assessment.
3) Implement the two censoring conventions from items 1) and 2) above. This will be the primary analysis only for the US regulatory consideration.
4) Analyses listed under Primary Analysis and Sensitivity/Supplementary Analyses items 1) - 3) will be repeated for the IRC assessment.
5) To address the intercurrent events of COVID-19 deaths, hypothetical strategy (Pre-PD deaths due to COVID-19 are censored) is implemented.
6) Unstratified log-rank test and unstratified Cox regression model to calculate HR and its 2-sided 95% CI; same censoring convention as the primary analysis.
Subgroup Analysis: Hazard ratio and its 95% CI from unstratified Cox regression model for each subgroup. Same censoring convention as for the primary analysis.
For the US, additional censoring conventions as specified for the US primary PFS analysis in item 3) above will be implemented.

Efficacy Endpoint	Definition	Analysis Method			
Secondary Endpoints					

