Time to next treatment (TTNT)	Time from the date of randomization to the date of the initiation of subsequent anti-cancer treatment. Post-treatment stem cell transplantation, CAR T-cell therapy, or other cellular therapies are not considered subsequent anti-cancer treatments for subjects responding to the treatment (CR or PR). Subjects without the use of subsequent anti-cancer treatment will be censored at the last follow-up date for subsequent anti-cancer therapy.	Method is the same as for the PFS analysis	
Time to worsening in FACT- Lym subscale ^{5,6}	Time from the date of randomization to the start date of worsening (defined by a ≥5 points reduction from baseline) in the Lym Subscale or death due to any cause, whichever occurs first.	Method is the same as for the PFS analysis	
	Subjects who have not met the definition of worsening will be censored at the last non-missing post-baseline PRO assessment. Subjects without baseline or post-baseline assessment will be censored at the date of randomization.		

Page 27 of 35

Efficacy Endpoint	Definition	Analysis Method			
	Exploratory Endpoints				
Progression- free Survival Based on Investigator Assessment after Initiation of Subsequent Anti-cancer Therapy (PFS2)	Time from the date of randomization to the date of the earliest of the following three types of events: • PD per investigator response assessment after administration of the first subsequent anticancer therapy • Death at any time on study • Initiation of the second subsequent anticancer therapy Subjects who did not experience a PFS2 event will be censored at the last adequate response assessment or the last follow-up for subsequent anti-cancer therapy (if they no longer have response assessments).	No inferential test will be conducted. For each treatment arm, the KM estimate of the median PFS2 (mPFS2) and the KM estimates at selected landmark points will be calculated using the same methods as for the primary PFS analysis.			

CMH: Cochran-Mantel-Haenszel; CI: confidence interval; CR: complete response; HR: estimate hazard ratio; ORR: overall response rate; OS: overall survival; PD: progressive disease; PFS: progression-free survival; PR: partial response.

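### The SAP's time-to-next-treatment event is any subsequent anti-cancer treatment, where the protocol specifies anti-lymphoma treatment, and the SAP does not list the change

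*SAP*

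**What the plan says.** Protocol 10.2.3 gives the endpoint as "TTNT, defined as the duration from the date of randomization to the start date of any anti-lymphoma treatment subsequent to study treatment". Protocol 10.2.6 uses the same anti-lymphoma wording for the treatment-naive arm.

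The TTNT row of SAP Table 2 (Section 4.2) reads "Time from the date of randomization to the date of the initiation of subsequent anti-cancer treatment". Its one exemption covers stem cell transplant, CAR T-cell and other cellular therapies in subjects who are responding. It says nothing about treatment for another malignancy.

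The term itself is described only in SAP 3.5: "Anti-cancer treatment includes anti-cancer drug therapies, anti-cancer radiation, and anti-cancer transplant/immunotherapy". The same section adds that "Subsequent anti-cancer treatments are anti-cancer treatments received after the date of the last dose of study treatment". Type of therapy and timing are given; the disease being treated is not.

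Three other provisions bear on the point:

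- SAP Section 1 says that the SAP prevails over the protocol where they differ, and that changes will be documented in Section 7. None of the seven items in Section 7 mentions the TTNT event.
- SAP 1.6.1 places TTNT second among the key secondary endpoints, after CR rate. For US purposes it follows OS.
- Protocol 11.4.5 has all new malignancies reported during treatment and follow-up, and SAP Section 5 summarizes other malignancies as a safety observation.

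**The concern.** TTNT is meant to show how long a subject goes before the lymphoma needs another treatment. A subject whose lymphoma is controlled, but who stops study drug and receives chemotherapy or radiotherapy for a new solid tumour, has not had that event under the protocol. Under the SAP as written, the subject has.

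The route is plausible. Protocol 1.2.4.8 names non-melanoma skin cancer as a risk with ibrutinib. Protocol 6.2.5 states: "Any non-study protocol-related chemotherapy, anticancer immunotherapy, experimental therapy, or radiotherapy are prohibited while the subject is receiving ibrutinib treatment". Drug or radiation treatment for a second cancer would therefore generally come after the last dose, which is what SAP 3.5 calls subsequent.

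At stake is a confirmatory test. Outside the US, TTNT must succeed before OS and ORR can be tested; for the US it must succeed before ORR. If second-cancer therapies occur at a similar rate in both arms, they pull the TTNT hazard ratio toward 1. Slightly more of them fall on the arm with longer lymphoma control, because its subjects stay at risk longer. If the handling is left open until a case arises, someone must decide it subject by subject, possibly after unblinding.

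**Working it through.** **Step 1: the definitions side by side.**

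| Item | Protocol 10.2.3 | SAP 3.5 and Table 2 |
|---|---|---|
| Start of clock | Randomization | Randomization |
| Event | Start of anti-lymphoma treatment | Start of anti-cancer treatment |
| Timing | After study treatment | After last dose of study treatment |
| Limited to lymphoma | Yes | No |
| Exemption | None stated | Cellular therapy in responders |
| Listed in SAP Section 7 | n/a | No |

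The conflict is in the event row and does not depend on any calculation.

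**Step 2: the plan's own figure.** The documents give no target hazard ratio or event count for TTNT, so I borrow the PFS planning values as a stand-in. With HR 0.61, one-sided alpha 0.025 and 80% power, Freedman's formula returns 134 events, matching SAP 1.4.1 (Schoenfeld's gives 129). The point does not affect that figure.

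**Step 3: effect on the TTNT hazard ratio.**

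Inputs from the documents: control median 14 months and HR 0.61 (both for PFS), 260 subjects randomized 1:1, so 130 per arm, and 21-month accrual.

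Assumptions not in the documents: exponential times; next-lymphoma-therapy hazards equal to the planned PFS hazards; second-cancer therapy at rate r = 0.5 to 3 per 100 person-years in both arms; data cut at 36 to 48 months.

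- Control hazard: ln 2 / 14 = 0.04951 per month.
- Combination hazard: 0.61 × 0.04951 = 0.03020 per month.
- HR with second-cancer therapies counted: (0.03020 + r) / (0.04951 + r), with r per month.
- r = 0.005/12 = 0.000417: 0.03062 / 0.04993 = 0.613.
- r = 0.03/12 = 0.0025: 0.03270 / 0.05201 = 0.629.

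**Step 4: number of extra events.** Let λ be the total hazard in an arm and T the cut in months. With uniform accrual over 21 months, mean time at risk per subject is (1/λ) × [1 − (e^(−λ(T−21)) − e^(−λT)) / (21λ)]. Multiply by 130/12 for person-years, then by r per year.

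| Cut, rate | Person-years, control / combination | Extra events, control / combination | Total |
|---|---|---|---|
| 36 months, 0.5 per 100 | 153.4 / 188.9 | 0.8 / 0.9 | 1.7 |
| 48 months, 3 per 100 | 177.2 / 232.2 | 5.3 / 7.0 | 12.3 |

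**Step 5: power, illustrative only.** Schoenfeld power is Φ(√(d/4) × |ln HR| − 1.96). With d = 134 borrowed from PFS, power is 81.6% at HR 0.61, 80.9% at 0.613 and 76.5% at 0.629.

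**The case against.** The best reply is that anti-cancer therapy is the trial's ordinary label for post-study lymphoma treatment. The protocol uses it in the follow-up provisions (3.1.1, 3.1.2, 7.2.2, 8.3.2), and Protocol 7.1.1.3 lists prior anticancer regimens within the disease history. SAP 3.5 sits in the subject-information section and may only be listing modalities for a summary table. A lymphoma-only intent is therefore possible. That stands as far as intent goes. But no such limit is written, the SAP's wording prevails, and the authors who wrote one exemption into the TTNT row did not write this one.

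It is also fair that the route is narrow. Surgery is not among the modalities in SAP 3.5, so an excised skin cancer would not clearly count. Treatment given during study drug is not subsequent. Protocol 4.1.2 excludes most subjects with a history of other cancers. The rate used above is assumed, and the dilution is toward the null when both arms share that rate.

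A reader might infer three stronger points, which the documents do not support:

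- **That US PFS censoring is also wrong.** Under SAP Table 2 item 1, which enters the US primary analysis through item 3, "subjects who received subsequent anti-cancer treatment will be censored at the last adequate post-baseline disease assessment". But the protocol's PFS definition and analysis (10.2.2, 10.5.1.1) contain no censoring rule for new therapy, so there is nothing to conflict with. Censoring at any systemic cancer therapy is defensible under a hypothetical strategy, since such therapy could also act on the lymphoma. Later progressions are not lost to the trial: Protocol 8.3.1 follows these subjects to progression, and SAP 4.1 makes treatment policy the US supplementary analysis and the primary analysis elsewhere.
- **That the CR and ORR window is wrong.** It uses the same broad term, but again against no contrary protocol rule. Narrowing it is a trade-off.
- **That TTNT loses its meaning.** A shift of 0.003 to 0.019 in the hazard ratio does not bear that out.

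**Conclusion.** The point holds for TTNT alone. The SAP's event is broader than the protocol's, the broader wording governs, and Section 7 does not record the change. As written, drug or radiation therapy given after the last dose only for a second malignancy is a TTNT event; the SAP does not say so expressly, but nothing in it excludes this.

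The expected effect is small and dilutes the treatment difference: HR from 0.61 to about 0.613 to 0.629, and about 2 to 12 extra events. This rests on the assumed rate of 0.5 to 3 per 100 person-years in both arms and on PFS planning values standing in for TTNT. The reason to act is the undeclared change to an alpha-controlled endpoint, which is cheap to settle before unblinding and awkward afterwards.

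**What to change.** In the TTNT row of SAP Table 2:

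1. Define the event as the start of subsequent treatment given for MCL, matching Protocol 10.2.3.
2. State that treatment given only for another malignancy is not a TTNT event, and that TTNT follow-up continues through it.
3. Assign the indication by blinded review of subsequent-therapy records in subjects with an other-malignancy entry, completed before unblinding.

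If the sponsor prefers the broader term, list it in Section 7 with a reason and add a lymphoma-only TTNT sensitivity analysis.

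No change is needed to the US PFS censoring rule, the response window, the sample size or the alpha.

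The cost is a few lines of SAP text and a review of what should be a small number of records. Other malignancies and subsequent therapies are already collected, so no new data items are expected.
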